Ultrasound Evaluation of Crohn's Disease

NCT03235180

September 28, 2017

IRB Minimal Risk Protocol Template

General Study Information

Principal Investigator: [name], [name], [name]

Study Title: Ultrasound Evaluation of Crohn's Disease

Protocol version number and date: 9/28/17

Purpose

Hypothesis: Small bowel stiffness and vascularity measured by ultrasound imaging are useful biomarkers for Crohn's disease.

Aims, purpose, or objectives:

The overall goal is to investigate the value of ultrasound measurements of small bowel stiffness and vascularity as new biomarkers for Crohn's disease.

Background (*Include relevant experience, gaps in current knowledge, preliminary data, etc.*):

Crohn's Disease (CD) is a chronic inflammatory condition in the bowel that affects over 1 million Americans, costing billions of dollars every year. Due to the relapsing nature of the disease, frequent imaging follow-ups are often necessary over many years to monitor treatment response to guide therapy adjustments. An ideal CD imaging method should be able to evaluate both inflammation and fibrosis, as patients with predominantly inflammatory lesions are more likely to respond to medical therapy, while patients with fibrostenotic lesions usually require surgery. Ultrasound is safe, cost-effective, and widely accessible, thus provides an attractive alternative to the clinical standard Computed Tomography (CT, risks of radiation) and Magnetic Resonance Imaging (MRI, more expensive and limited accessibility). Because ultrasound may not be able to image bowel loops deep in the body, its main role is to follow-up after initial screening by CT or MRI (especially for terminal ileum, which is easily accessible by ultrasound and the most frequently affected bowel segment for CD).

In this project, we will study the efficacy of ultrasound shear wave elastography and vascularity imaging for CD evaluation. Literature evidences demonstrate that bowel stiffness is correlated with fibrosis, while bowel vascularity and perfusion is correlated with inflammation. Therefore, we expect the combination of shear wave elastography and vascularity imaging can increase the sensitivity and specificity of CD evaluation.

Aim 1: To evaluate the correlation of ultrasound measurements with clinically indicated Magnetic Resonance Enterography (MRE).

Aim 2: To investigate if ultrasound measurements can be used to predict treatment response for Crohn's disease.

Subject Information – charts, records, images, or specimens are considered ‘subjects’

Target accrual is the proposed number of subjects to be included in your study at your site. “Subjects” may include Mayo Clinic charts, records, or specimens, and/or charts, records, or specimens received at Mayo Clinic from external sources for collaborating analysis by the investigator under this IRB application:

Target accrual: 100

Subject population: patients with confirmed or suspected Crohn’s disease.

Inclusion criteria: Crohn’s disease patients with involvement of terminal ileum (thickness > 3mm) or other segments of small or large bowel, age above 18.,

Exclusion criteria: patients with change of medicine or going to surgery over the 6-months follow-up period, patients with unreliable ultrasound images due to conditions such as large body habitus or poor ultrasound imaging window; adults lacking capacity to consent; vulnerable subjects such as prisoners. Pregnant women, nursing mothers, patients with known or suspected right-to-left, bi-directional, or transient right-to-left cardiac shunts, patients with history of hypersensitivity allergic reactions to ultrasound contrast agents.

Yes No Will a Certificate of Confidentiality (COC) be obtained from NIH? If yes,

Who is obtaining the COC: Mayo Clinic investigator, study sponsor, other:

Explain why a COC is needed:

Study Design

Methods: *Describe, in detail, the research activities that will be conducted under this protocol:*

Study Design: We will study the terminal ileum of 100 Crohn’s disease patients to investigate the efficacy of ultrasound measurements for disease evaluation and treatment outcome prediction. Patients with ongoing medical therapy or starting a new medical therapy will be recruited. Inflammation and fibrosis evaluated by contrast enhanced MR enterography at baseline and 6-months post therapy will be used as the reference standard. Ultrasound will be performed at baseline, 4-weeks, and 6-months. For Aim 1, correlation of ultrasound measurements with MR enterography results will be evaluated at baseline and 6-months. For Aim 2, we will assess the association of the percentage change in ultrasound parameters from baseline to 4-weeks with the percentage change in MR enterography scores from baseline to 6-months. More information about data analysis can be found in the statistical section below.

Ultrasound Procedure: Patients will be fasting for 4 hours before ultrasound scans to reduce bowel air and peristalsis. The ultrasound transducer will be sanitized as per clinical routine before each use. The terminal ileum (TI) will be located by B-mode ultrasound. The TI lesion with the most significant thickening will be

identified in B-mode images for subsequent measurements. Repeated measurements of shear wave speed (which represents bowel stiffness) at the TI lesion will be obtained using the GE Logiq E9 ultrasound scanner. Vascularity images of the TI lesion will be obtained using the Verasonics ultrasound scanner. We will obtain ultrasound images before and after the administration of contrast microbubbles to evaluate the benefit of contrast agents. Lumason, a FDA approved ultrasound contrast agent for liver imaging, will be used (IV injection) for this study. The subject will be instructed to briefly hold his/her breath during each ultrasound acquisition. Sometimes it can be difficult to find the same bowel lesion for imaging for longitudinal studies. We will measure the distance of the lesion from the ileocecal valve and use this information to help locating the same lesion for longitudinal studies.

Safety of Lumason Administration: Lumason is approved by FDA as an ultrasound contrast agent for routine clinical use. In this study, the dosage and route of administration of Lumason will comply with the guideline of the package insert of Lumason. Our study team member will screen participants to exclude pregnant women, nursing mothers, patients with known or suspected right-to-left, bi-directional, or transient right-to-left cardiac shunts, patients with history of hypersensitivity allergic reactions to ultrasound contrast agents. If a female patient with childbearing potential is not sure of her pregnancy status, a urine pregnancy test will be done. Potential side effects will be monitored by sonographer and/or radiologists: Radiology has protocols on how to respond to adverse reaction of Lumason and Definity ultrasound contrast agents

Resources: *Describe the available resources to conduct the research (personnel, time, facilities, mentor commitment, etc.):*

We have commitments from all participating personnel. Patients will be referred and recruited by participating physicians. We have a GE Logiq E9 and a Verasonics ultrasound scanner that can be used for this study.

Check all that apply. If none apply, leave blank:

This is a multisite study involving Mayo Clinic and non-Mayo Clinic sites.
When checked, describe the research procedures/activities being conducted **only** at Mayo Clinic:

Mayo Clinic staff will be engaged in research activity at a non-Mayo Clinic site. *When checked, provide the location and a detailed description of the Mayo Clinic research staff involvement.*

This study is to establish and/or maintain an ongoing database or registry for research purposes only.

The research involves contact or interaction with subjects, for example, surveys, questionnaires, observation, blood draw.

The study involves photographing, audiotaping or videotaping subjects (and guests).

Blood Collection

If this study involves prospective blood collection by finger, heel, ear stick or venipuncture, complete the following:

From healthy, non pregnant, adult subjects who weigh at least 110 pounds. For a minimal risk application, the amount of blood drawn from these subjects may not exceed 550ml in an 8 week period and collection may not occur more frequently than 2 times per week.

Volume per blood draw: _____ ml

Frequency of blood draw (e.g. single draw, time(s) per week, per year, etc.) _____

From other adults and children considering age, weight, and health of subject. For a minimal risk application, the amount of blood drawn from these subjects may not exceed the lesser of 50 ml or 3 ml per kg in an 8 week period, and collection may not occur more frequently than 2 times per week.

Volume per blood draw: _____ ml

Frequency of blood draw (e.g. single draw, time(s) per week, per year, etc.) _____

Review of Chart, Images, Specimens

Provide the date range for collection of data and/or specimens that will be included in your research dataset.
Example: 01/01/2000 to 12/31/2013 or all records through mm/dd/yyyy.

4/1/2017 to 4/1/2025

For a retrospective chart review, enter the date range:

Check all that apply:

This study involves only data and/or specimens that exist at the time this application is submitted to the IRB (IRB submission date). No data or specimens will be collected beyond this date.

This study involves only data and/or specimens that will be collected after submission to the IRB.

The study involves data and/or specimens that exist at the time of submission to the IRB **and** data and/or specimens that will be collected after submission to the IRB, for example a study that includes collection of existing data and prospective collection of specimens.

Data and/or specimens used in this study are collected under another IRB protocol. *When checked, provide the IRB number(s) from which the research material will be obtained. When appropriate, check the box below to attest that subjects have provided consent for future use of their data and/or specimens, as described in this protocol.*

IRB Number/s - Data Only: _____

IRB Number/s - Specimens Only: _____

IRB Number/s - Data and Specimens: _____

Note: When subjects provided consent for use of their data and/or specimens, as described in this protocol.

Other data sources will be utilized in this study, e.g. receiving data/specimens from an external party. When checked, provide all data sources:

Data Confidentiality, HIPAA Subject Identifiers

Review the list of subject identifiers below and, if applicable, check the box next to each subject identifier being recorded at the time you are collecting/abstracting data/specimens for use in this study.

Subject Identifiers: Individually identifiable information, including demographic data, that identifies the individual or for which there is reasonable basis to believe it can be used to identify the individual. NOTE: Identifiers apply to subjects enrolled in your study and to the subject's relatives, household members, employers, etc.

Internal refers to subject identifiers that will be included in the dataset maintained by the study team.

External refers to subject identifiers that will be shared with persons outside of the immediate study team, for example, sent to an external collaborator or shared with a national registry.

SUBJECT IDENTIFIERS Check all that apply	INTERNAL IDENTIFIER	EXTERNAL IDENTIFIER
Name	x	
Social Security number		
Medical record/patient registration number, lab accession, specimen or radiologic image number	x	
Study number, subject ID, or any other unique identifying number, characteristic or code that can be used to link the identity of the subject to the data	x	
Dates: All elements of dates [month, day, and year] directly related to an individual. Their birth date, date of death, date of diagnosis, etc. Note: Recording a year only is not a unique identifier.	x	
Medical device identifiers and serial numbers		
Biometric identifiers, including finger and voice prints, full face photographic images and any comparable images		
Web Universal Resource Locators (URLs), Internet Protocol (IP) address numbers, email address		
Street address, city, county, precinct, zip code, and their equivalent geocodes		
Phone or fax numbers		
Account, member, certificate or professional license numbers, health beneficiary numbers		
Vehicle identifiers and serial numbers, including license plate numbers		
If None of the above identifiers will be recorded or maintained in the dataset and/or sent outside of the study team, please check "None".	 None	 None

Statistical Information

Note: Power analyses and study endpoints are not needed for a pilot or feasibility studies.

No statistical information. *If checked, please explain:*

Statistical Considerations

Power Statement:

The sample-size for the present investigation was determined for the primary aim of assessing the correlation between ultrasound parameters and the MaRIA score (a score calculated from MR enterography, which reflects bowel inflammation [1]). For ultrasound to have meaningful clinical utility we would require a correlation with MaRIA score of at least 0.70. For the primary analysis, the correlation between ultrasound measurements and MaRIA score will be compared to 0.70 using a two-tailed, alpha=0.05 level test. Under the assumption that the “true” correlation is 0.82, a sample-size of N=100 will provide statistical power of 82% for the primary analysis.

Data Analysis Plan:

Disease activity measurements will be obtained via MR enterography at baseline and 6-months following treatment, and via ultrasound at baseline, 4-weeks and 6-months after treatment. Two quantitative ultrasound parameters will be obtained: A) shear wave speed obtained from the GE Logiq E9; B) vessel density (the percentage of pixels in the bowel lesion with blood flow compared to the total area of the lesion) obtained from the Verasonics. For each ultrasound parameter, the mean of all repeated measurements will be used as the representative value for a given patient at a given time. Measurements obtained following baseline will be expressed as percentage change from baseline. For inflammation evaluation, the correlation of each ultrasound parameter with MaRIA score will be assessed using a point estimate and 95% confidence interval. In addition, using a MaRIA cut-point of 11, patients will be categorized as having mild versus severe disease [1]. As a secondary analysis, logistic regression with corresponding ROC (Receiver Operating Characteristic) analysis will be used to assess whether ultrasound measurements can distinguish between mild versus severe inflammation. Findings from these analyses will be summarized using the point-estimate and 95% confidence interval for the area under the ROC curve (AUROC). In addition to univariate analyses, exploratory multivariable analyses will be performed to assess whether combination of ultrasound parameters can increase the performance relative to the univariate findings. Similar analyses will be performed to assess whether ultrasound parameters are useful for fibrosis evaluation: for these analyses, the MR enterography percentage gain change (PGC) will be used for correlation analysis, and a PGC cut point of 23.5% will be used to categorize fibrosis as mild or severe for ROC analysis [2].

For Aim 2, a series of analyses will be performed to assess whether ultrasound parameters obtained at baseline and 4-weeks can predict 6-month treatment outcome. A correlation analysis will be performed to assess the association of the percentage change in ultrasound parameters from baseline to 4-weeks with the percentage change in MaRIA score from baseline to 6-months. In addition, treatment outcome will be dichotomized (responder, non-responder) based on the 6-month MR enterography. Univariable and multivariable logistic

regression with corresponding ROC analyses will be used to assess whether percentage change in ultrasound measurements at 4-weeks can predict treatment outcome. Findings from these analyses will be summarized using the point-estimate and 95% confidence interval for the AUROC. In all cases, distributional assumptions will be evaluated with transformations or non-parametric methods used as appropriate. Two-tailed p-values < 0.05 will be considered statistically significant.

Endpoints

Primary: please see detailed description above.

Secondary: please see detailed description above.

References:

1. Rimola, J., et al., *Magnetic Resonance Imaging for Evaluation of Crohn's Disease: Validation of Parameters of Severity and Quantitative Index of Activity*. Inflammatory Bowel Diseases, 2011. **17**(8): p. 1759-1768.
2. Rimola, J., et al., *Characterization of Inflammation and Fibrosis in Crohn's Disease Lesions by Magnetic Resonance Imaging*. American Journal of Gastroenterology, 2015. **110**(3): p. 432-440.

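### The exclusion for a medicine change or surgery during follow-up can be settled only after enrolment, and the plan does not say which analyses it applies to

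*Combined protocol and SAP*

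**What the plan says.** The exclusion list under Subject Information opens with "Exclusion criteria: patients with change of medicine or going to surgery over the 6-months follow-up period". It has no qualifier limiting this to changes planned or expected at entry. The same section gives "Target accrual: 100", and Study Design says "We will study the terminal ileum of 100" Crohn's disease patients, either on existing therapy or starting a new one.

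For Aim 1, Study Design says "correlation of ultrasound measurements with MR enterography results will be evaluated at baseline and 6-months". The Power Statement says "a sample-size of N=100 will provide statistical power of 82% for the primary analysis". It does not say whether that analysis uses baseline or 6-month data.

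For Aim 2, the Data Analysis Plan says "treatment outcome will be dichotomized (responder, non-responder) based on the 6-month MR enterography" and uses logistic regression with ROC analysis to "assess whether percentage change in ultrasound measurements at 4-weeks can predict treatment outcome".

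Neither the Power Statement nor the Data Analysis Plan defines an analysis set, a replacement rule, or the handling of a patient who changes medicine or has surgery after enrolment. The Endpoints entry is only "Primary: please see detailed description above".

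**The concern.** An entry criterion should be decidable at entry. This one refers to what happens over the following six months, so under its plain wording a patient can be enrolled, scanned at baseline and 4 weeks, and then become excluded. The two aims are affected differently.

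- **Aim 1.** A change of medicine or an operation in month three cannot alter an ultrasound/MRE pair obtained at baseline. Dropping that pair loses information and selects the sample on a later event, with no gain in validity.
- **Aim 2.** The prediction is made from the change at 4 weeks. If only patients who reach 6 months without a change or surgery are analysed, the estimate is conditional on something nobody knows at 4 weeks. The result would then describe a group that cannot be identified when the prediction is used. The Background says that imaging guides therapy adjustment and that fibrostenotic lesions usually lead to surgery, so a link between removal and response is plausible.

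Because the scope of the exclusion is not fixed in advance, the choice of whom to drop could also be made after the results are known.

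**Working it through.** **1. Can the clause be applied at entry?** Patients starting a new therapy are recruited, so that initial change is not what is excluded; the clause concerns what follows. A reading limited to changes already planned is possible, but the text does not state it. Nothing in the statistical section resolves the matter: its one general handling sentence concerns distributional assumptions.

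**2. Reproduce the stated power.** Inputs from the Power Statement: null correlation 0.70, assumed true correlation 0.82, two-sided alpha 0.05, N=100.

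Power = Φ[(atanh 0.82 − atanh 0.70) × √(N−3) − 1.960]

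atanh 0.82 = 1.1568; atanh 0.70 = 0.8673; difference 0.2895.

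N=100: 0.2895 × √97 = 2.851; 2.851 − 1.960 = 0.891; Φ = 81.4%. Simulating the same test on bivariate normal data gives about 82.5%. The stated 82% is reproduced.

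**3. Power if baseline pairs are lost.** The documents give no rate of medicine change or surgery, so 10, 20 and 30% are assumptions.

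| Pairs analysed | Fisher z | Simulation |
|---|---|---|
| 100 | 81.4% | 82.5% |
| 90 | 77.0% | 78.5% |
| 80 | 71.9% | 73.6% |
| 70 | 65.9% | 67.8% |

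The point where power drops below 80% depends on the method. By Fisher z it is 4 lost pairs (N=97: 80.2%; N=96: 79.7%). By simulation it is about 7 (N=94: 80.2–80.3%; N=93: 79.8%).

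The table applies only if all four of these hold: the powered test uses baseline pairs; 100 counts enrolled patients; the pairs of later-excluded patients are dropped; and those patients are not replaced.

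**4. If 100 means evaluable.** Power is unchanged and the cost moves to enrolment: 100/0.90 = 112, 100/0.80 = 125, 100/0.70 = 143 (rounded up).

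**5. Aim 2, illustration only.** None of these inputs comes from the documents. Latent response z is standard normal, and a responder has z > 0 (50%). The 4-week change is 0.6z + 0.8 × noise. Patients with the highest 10, 20 or 30% of −kz + √(1−k²) × noise are removed.

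- Full sample: AUROC 0.779, 95% CI half-width 0.091 for 100 patients.
- Removal unrelated to response (k=0): AUROC unchanged; half-width 0.096/0.102/0.109 from the smaller sample alone.
- Removal of poorer responders: AUROC 0.772/0.769/0.767 at k=0.5, and about 0.765/0.757/0.753 at k=0.7.
- Removal of better responders (k=−0.5): 0.772/0.769/0.767.
- For comparison, keep everyone, and assume that those who changed respond at 30–50% regardless of their response to the first therapy. With k of 0.5–0.7, AUROC is then about 0.69–0.76.

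In this model the restriction moves AUROC by 0.026 at most, less than the half-width of its interval. Adding patients who changed can move it more, because their 4-week scan and 6-month MRE reflect different therapies.

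**The case against.** The strongest reply is that the clause is itself the handling rule: such patients are out, and the aim is to study stable therapy. The next item in the list, unreliable ultrasound images, may also become known only after scanning, so the list seems to double as an evaluability list. The form defines target accrual as the number of subjects to be included, which fits excluded patients not counting toward 100. Nothing forbids replacement, and the data collection window is long. On that reading no power is lost.

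Much of this stands. A stable-therapy analysis is a legitimate target, and the accrual wording leans toward 100 included patients. The reply does not explain why an intact baseline pair should be discarded, and it does not make the Aim 2 condition known at 4 weeks.

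Three stronger readings are tempting, and the documents support none of them.

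- **That the primary test is underpowered.** This needs all four conditions in step 3, and the documents establish none of them.
- **That Aim 2 is biased in a known direction.** The Background makes a link to response plausible but gives neither size nor sign. In the illustration, removal in either direction lowers AUROC slightly.
- **That all patients, including those who changed therapy, should form the main Aim 2 analysis.** That is a different estimand with its own distortion, as step 5 shows.

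**Conclusion.** The point holds and should be fixed. It is certain that the criterion, as worded, turns on events after enrolment and that no analysis set limits its reach. Applied literally, it discards valid baseline pairs from Aim 1 and makes the Aim 2 result conditional, without saying so, on a status unknown at the time of prediction.

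The numerical consequence is less certain. The plan's 82% is correct for its own inputs. The fall to between 66% and 79% rests on assumed losses of 10–30% and on the four conditions; if 100 means evaluable, the loss is zero. For Aim 2 the documents support a concern about interpretation and not a figure for bias.

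**What to change.** 1. Word the criterion so that at entry it covers only changes of medicine or surgery already planned. State whether N=100 is enrolled or evaluable, and whether the powered test uses baseline or 6-month data.
2. Aim 1: keep every baseline ultrasound/MRE pair, whatever happens later.
3. Aim 2: label the unchanged-therapy analysis as conditional on no medicine change or surgery by 6 months. Report the number, timing and reasons of those left out. Alongside it, show a sensitivity analysis of all patients with a 4-week ultrasound and a 6-month MRE. Which of the two is the main estimand is for the sponsor to decide and to state in advance.

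This concerns eligibility wording and analysis only; no rule for treating patients is proposed.

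**Cost.** Wording changes, and chart abstraction of the date and reason for each change or operation. Enrolment rises only if the sponsor decides that 100 means evaluable. Some 6-month MREs in the sensitivity analysis will reflect more than one therapy, and some will not exist, for example after resection or because the MRE is done only when clinically indicated. If follow-up would otherwise have stopped at the change, continuing it means further study ultrasounds with contrast.

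### Aim 2 pools patients on ongoing therapy with new starters and has no term or stratum for therapy status, so a pooled association alone cannot show that early ultrasound change predicts response.

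*Combined protocol and SAP*

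**What the plan says.** The Purpose section gives Aim 2 as: "To investigate if ultrasound measurements can be used to predict treatment response for Crohn's disease". Under Study Design, the terminal ileum is studied in 100 Crohn's "disease patients to investigate the efficacy of ultrasound measurements for disease evaluation and treatment outcome prediction", and the next sentence reads: "Patients with ongoing medical therapy or starting a new medical therapy will be recruited". No text limits Aim 2 to one of the two groups, and no mix or quota is given.

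The exclusion criteria remove "patients with change of medicine or going to surgery over the 6-months follow-up period". That concerns changes during follow-up. As worded it removes neither patients on stable ongoing therapy nor patients who begin a therapy at entry.

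The Aim 2 part of the Data Analysis Plan states: "A correlation analysis will be performed to assess the association of the percentage change in ultrasound parameters from baseline to 4-weeks". The other variable in that correlation is the relative change in MaRIA over the 6 months. The plan then classifies patients as responders or non-responders from the 6-month MR enterography and uses univariable and multivariable logistic regression with ROC to "assess whether percentage change in ultrasound measurements at 4-weeks can predict treatment outcome". The covariates of the multivariable model are not listed. In the parallel Aim 1 text, multivariable analysis means combining ultrasound parameters. The section closes with: "Two-tailed p-values < 0.05 will be considered statistically significant". Therapy status does not appear as a covariate, stratum, subgroup or sensitivity analysis.

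**The concern.** Only one of the two groups starts treatment at baseline. It is plausible, though the documents give no data, that new starters change more than ongoing patients on ultrasound at 4 weeks and on MaRIA at 6 months. Therapy status is then a common cause of both variables. The pooled correlation and the pooled AUROC would partly reflect who had just started treatment, which is known without a scan.

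The error can also run the other way. If early ultrasound change is informative only in new starters, ongoing patients dilute it and a real signal can be missed. In both cases the pooled result does not answer the Aim 2 question.

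**Working it through.** **The plan's own figure.** The only power statement is for Aim 1: true correlation 0.82 against 0.70, N=100, two-sided alpha 0.05, 82% power. By Fisher z, (atanh 0.82 − atanh 0.70) × √97 − 1.96 = 0.2895 × 9.849 − 1.96 = 0.891, and Φ(0.891) = 81.4%. The figure reproduces. It does not cover Aim 2, which has no power statement.

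**Inputs for Aim 2.** From the documents: N=100 and two-sided p < 0.05. Assumed, because the documents are silent: share of new starters p = 0.2, 0.3 or 0.5; mean shifts of new starters dx (ultrasound change) and dy (MaRIA change) in within-group SDs; response rates by group.

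**Pooled correlation with zero within-group correlation.** With q = p(1−p),

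r = q·dx·dy / √[(1 + q·dx²)(1 + q·dy²)]

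P(p < 0.05) = Φ(atanh(r)·√97 − 1.96) + Φ(−atanh(r)·√97 − 1.96)

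Example: p = 0.3, dx = dy = 1. Then q = 0.21, r = 0.21/1.21 = 0.174, atanh(r)·√97 = 1.73, and P = Φ(−0.23) = 41%.

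| Shift on both (SD) | p = 0.2: r, P | p = 0.3: r, P | p = 0.5: r, P |
|---|---|---|---|
| 0.5 | 0.038, 7% | 0.050, 8% | 0.059, 9% |
| 0.8 | 0.093, 15% | 0.118, 22% | 0.138, 28% |
| 1.0 | 0.138, 28% | 0.174, 41% | 0.200, 52% |
| 1.5 | 0.265, 76% | 0.321, 91% | 0.360, 96% |

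- Unequal shifts (0.5 SD ultrasound, 1.0 SD MaRIA): r = 0.073, 0.093, 0.108 and P = 11%, 15%, 19% for p = 0.2, 0.3, 0.5.
- Only one change shifts: r = 0 and P about 5%.
- Therapy-adjusted (partial) correlation, by simulation: P = 4.6% to 5.8%.
- Shift needed for the artefact alone to reach the Aim 1 bar of r = 0.70: √[(0.7/0.3)/q] = 3.06 SD at p = 0.5 and 3.82 SD at p = 0.2.

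**Pooled AUROC with no within-group signal.** Let w and v be the shares of new starters among responders and non-responders. Then AUROC = 0.5 + (w − v)·[Φ(d/√2) − 0.5]. Example: p = 0.3, response 60% (new) against 20% (ongoing), d = 1. w = 0.18/0.32 = 0.5625, v = 0.12/0.68 = 0.1765, AUROC = 0.5 + 0.386 × 0.260 = 0.60.

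- Response 60% vs 20%: 0.54–0.56, 0.58–0.61 and 0.61–0.65 at 0.5, 1.0 and 1.5 SD.
- Response 50% vs 30%: 0.52–0.53, 0.54–0.55 and 0.55–0.57.
- Equal response: 0.50.
- Therapy status alone, 0.5 + (w − v)/2: 0.66–0.71 at 60% vs 20%.

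**Dilution.** Suppose r = 0.5 in new starters, 0 in ongoing patients, and no mean shift. Pooled r = 0.5p = 0.10, 0.15, 0.25, with Fisher z power 17%, 32%, 71% at N=100. Among new starters alone (n = 20, 30, 50), Φ(atanh(0.5)·√(n−3) − 1.96) = 62%, 81%, 96%. Adding therapy status as a covariate does not recover this (17%, 32%, 70% by simulation); within-group reporting does.

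**The case against.** The strongest reply is that the size is entirely assumed. The artefact needs a difference on both changes, and at 0.5 SD it is only 7–9% against 5%. Zero within-group correlation is also the most adverse case. With a within-group r of 0.3, 30% new starters and 1 SD shifts, pooled r is (0.30 + 0.21)/1.21 = 0.42. The pooled test then rejects about 99% of the time, against about 86% for a true r of 0.30, so the estimate is inflated but the significance conclusion usually stands. This is right, and it means the false-positive risk is mainly a risk when within-group association is near zero. That is the null which Aim 2 must rule out.

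Second, the pooled association is a legitimate description of the recruited cohort, and rejecting zero for it is then no error. This stands for the pooled result as description. It does not support a claim that ultrasound change predicts response beyond knowing who has just started therapy.

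Third, the exclusion for change of medicine might be read as removing new starters, and the timing of follow-up relative to therapy is unclear for patients already treated. But reading the exclusion that way contradicts the recruitment sentence, so the passages need reconciling either way.

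Fourth, the unlisted multivariable model might include therapy status. The text does not say so, and the correlation and univariable ROC would remain unadjusted.

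Finally, a yes/no therapy flag may leave residual confounding, since ongoing therapy can vary in duration. That limits the remedy but does not favour omitting the flag.

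**Conclusion.** The concern holds. As written, Aim 2 can reach p < 0.05 with no prediction inside either therapy group, and it can miss a signal confined to new starters. The gap in the plan is certain; its size is not. Under the assumed 20–50% new starters and no within-group correlation, the error rate is 7–9% at 0.5 SD shifts, 28–52% at 1.0 SD and 76–96% at 1.5 SD. It is about 5% if the groups differ on only one change or if therapy status is adjusted for. Artefactual AUROCs are modest, 0.52 to 0.65 over the unequal response rates tried. The consequence is confined to the Aim 2 inference. The plan should be changed here because the remedy is cheap and bears directly on the Aim 2 question.

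**What to change.** 1. State whether both therapy groups enter Aim 2, and reconcile the recruitment sentence, the change-of-medicine exclusion and the time origin of the 6-month assessment for patients already on therapy.
2. Record therapy status (new or ongoing) at baseline.
3. Pre-specify it as a covariate in the Aim 2 correlation (partial correlation or regression) and in the logistic models.
4. Report adjusted and within-group correlations beside the pooled one.
5. For ROC, report within-group AUROCs and the gain of therapy status plus ultrasound over therapy status alone. The AUROC of a model that merely includes the covariate also contains that covariate's own discrimination.
6. Keep the pooled result as a description of the cohort, and do not base a claim of prediction on it alone.

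The cost is wording, one variable known at enrolment and one degree of freedom: the correlation detectable with 80% power moves from 0.277 to 0.278. The real downside is precision within groups. The 95% half-width for r near zero, tanh(1.96/√(n−3)), is 0.28 at n=50, 0.36 at n=30 and 0.44 at n=20, against 0.20 at n=100. For a within-group AUROC with 20 new starters at 60% response (12 against 8), the null standard error is √[21/(12·12·8)] = 0.135, a half-width of about 0.26. With two ultrasound parameters and two groups, the within-group results should be presented as estimates with intervals.
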